4. Perform inhaler re-training using sham capsules with the CVT-301 inhaler and IFU. If the patient has undergone inhaler training in both the ON and OFF states at SV1, it may be done in either state at this visit.
5. Patient training on assessment of the ON/OFF state will be repeated.
6. Distribute a new PD Diary and Screening ON/OFF Episodes Log, and instruct the patients to complete both of them for the 3 consecutive days prior to TV1.
7. If needed, the following assessments from SV1 may be completed or repeated: MMSE (in ON state); full physical examination; 12-lead ECG; standard vital signs (BP, HR, and RR) and orthostatic vital signs (BP and HR); spirometry (in ON and OFF states); UPDRS Parts 1, 2 and 4 (in an ON state); UPDRS Part 3 (in ON and OFF states); ON/OFF concordance testing (in ON and OFF states); and clinical laboratory test, including serum pregnancy test, if applicable (with documentation of fasting status).
8. Complete the C-SSRS, Epworth Sleepiness Scale, and QUIP (preferably in an ON state).
9. Monitor for AEs throughout the visit.

10. Schedule a DLco assessment to be performed at an outside pulmonary laboratory after SV2 and prior to TV1. The assessment should be performed while the patient is in an ON state (as reported by the patient to the pulmonary technician) at the pulmonary function facility. As part of the procedure, a slow vital capacity maneuver will be performed, followed by DLco, and then spirometry.

If a patient is unable to complete a screening assessment at SV2, an additional visit (repeat SV2) may be scheduled prior to eligibility determination and randomization. Any repeat assessments should be performed in the respective motor state as described for SV1. The site will contact patients by telephone 4 to 6 days prior to TV1 to confirm the DLco assessment has been done, to confirm the next study visit, and to remind patients of the study procedures required prior to the next scheduled study visit (including completion of the PD Diary and Screening ON/OFF Episodes Log). In addition, the site should remind the patients during the call that they must be symptom-free of any flu-like syndrome or other respiratory infection for at least 3 days prior to TV1 and that they should contact the site if an intervening illness occurs prior to TV1. If the patient has any of these symptoms within this time period, this visit will be rescheduled once these symptoms have been resolved for at least 3 days.

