- Distribute the Inhaled Dosing Log and review instructions for completion for recording the number of times the inhaler was used and the number of capsules used

for each inhalation treatment (to be completed daily throughout the 13-month treatment period).

- Distribute study drug kits to patients. Instruct patients to collect used empty capsules and return them at the next visit along with the PD Diary, Inhaled Dosing Log, and other study supplies.

Study Drug Dosing

Immediately pre-dose, perform a spirometry assessment (record the patient's ON/OFF state on the spirometry source record). Under clinic staff supervision, preferably between 2 and 5 hours after receiving their standard dose of PD medication (in the OFF state), patients will prepare and self-administer their first dose of blinded study drug from the study drug kits provided (i.e., 2 capsule inhalations of either CVT-301 DL1 or CVT-301 DL2). Patients will be permitted sips of water between capsule inhalations as needed.

Note: Instructions for how to properly use the CVT-301 system are outlined in the Instructions for Use document that is included with every CVT-301 study kit. Refer to [Appendix 17](#) for additional system information.

Post-dose (10 – 60 minutes)

The following post-dose safety evaluations will be performed:

- Record vital signs (standard and orthostatic BP and HR) at 20 and 60 minutes post-dose.
- Record RR at 10, 20, 30, and 60 minutes post-dose.
- Evaluate spirometry at 15, 30, and 60 minutes post-dose. At the time of each spirometry assessment, clinic staff will record the patient's motor state. If within the first 60 minutes after inhalation, the patient's spirometry assessment shows either of the following, the patient will NOT be sent home with study drug, and the site will follow the Spirometry Alert and Review Process: a decrease in FEV1 $\geq 20\%$ AND a decrease in FEV1 by 200 mL compared with pre-dose results, and/or a reduction in the FEV1/FVC ratio to $<60\%$. If either criteria are met, the patient will NOT be sent home with study drug and the procedures described in [Appendix 18](#) will be followed.
- Monitor for AEs throughout the visit.

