The next visit will be scheduled. Clinic staff will also schedule the DLco and spirometry visit within 2 weeks prior to TV3. These assessments should be performed in an ON state (as reported by the patient to the pulmonary technician) in the pulmonary function facility. As part of the procedure, a slow vital capacity maneuver will be first, followed by DLco, and then spirometry. Clinic staff will arrange to speak with patients by telephone 1 week before TV3 to address any concerns or challenges with the inhaler systems, PD Diary, or Inhaled Dosing Log, to monitor for any AEs, to confirm the DLco and spirometry visit at the pulmonary function lab has been done/scheduled, to confirm the next study visit, to ask the patients how many empty study drug kits will be returned at the next visit, and to remind patients of the study procedures required before the next visit (including completion of the PD Diary and Inhaled Dosing Log).

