Spirometry equipment will be provided to each study site to perform all spirometry assessments for CVT-301-naïve patients and [CVT-301-009](#) patients at SV1, SV2 (if necessary) and TV1 (all patients). All other spirometry assessments will be collected during the DLco and spirometry visits that take place at the pulmonary function lab. Spirometry data collected at pulmonary function labs will be reviewed immediately by a pulmonologist on site for safety signals and then sent to and reviewed by a central Pulmonary Function Testing reviewer (TechEd Consultants).

11.1.7. Carbon Monoxide Diffusing Capacity (diffusing capacity of the lungs for carbon monoxide-DLco)

Patients will undergo DLco assessments, which will be acquired in accordance with ATS criteria ([Miller et al., 2005](#)), at a dedicated pulmonary function facility after SV2 (and prior to TV1; 301-naïve patients and [CVT-301-009](#) patients), within 2 weeks prior to TV3, TV4, TV5, and TV6, and at 4 to 5 weeks after TV6, as described in the [Appendix 3](#) through [Appendix 10](#). These assessments should be performed while the patient is in the ON state (as reported by the patient to the pulmonary technician). Pulmonary function facility technicians will perform a slow vital capacity maneuver, followed by DLco, and then spirometry. The pulmonary facilities will use

their own equipment to perform all necessary pulmonary function testing relevant to DLco acquisition.

DLco and slow vital capacity maneuvers will be assessed and processed in accordance with ATS/ERS standards. Spirometry procedures will be conducted at the same visits in the same manner as those conducted at clinical sites in accordance with ATS criteria (see [Section 11.1.6](#)).

All DLco data collected at pulmonary function labs will be sent to and reviewed by a central Pulmonary Function Testing reviewer (TechEd Consultants).

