## Statistical Analysis Plan

### 4. ENDPOINTS

#### 4.1. PRIMARY ENDPOINT

The primary endpoints related to the primary objective of the study are the pulmonary safety measures, FEV1, FVC and FEV1/ FVC ratio, assessed over a 12 month period. FEV1, FVC and FEV1/FVC ratio will be recorded from the single “best test” (based on effort with highest summed FEV1 and FVC). Variables will include the absolute FEV1, FVC, and FEV1/FVC ratio and FEV1 and FVC expressed as % of predicted value. Changes from baseline (TV1) for each variable will be calculated at each subsequent visit.

Percent Predicted =  $100 * (\text{Observed}) / \text{Predicted}$ , where predicted values are calculated using the formulae by [Hankinson et al \(Spirometric Reference Values from a Sample of the General U.S. Population, 1999\)](#):

Caucasian males  $\geq 20$  years of age:

- FVC predicted =  $-0.1933 + 0.00064 * \text{age} - 0.000269 * \text{age}^2 + 0.00018642 * \text{height}^2$
- FEV1 predicted =  $0.5536 - 0.01303 * \text{age} - 0.000172 * \text{age}^2 + 0.00014098 * \text{height}^2$

Caucasian females  $\geq 18$  years of age:

- FVC predicted =  $-0.3560 + 0.01870 * \text{age} - 0.000382 * \text{age}^2 + 0.014815 * \text{height}^2$
- FEV1 predicted =  $0.4333 - 0.00361 * \text{age} - 0.000194 * \text{age}^2 + 0.00011496 * \text{height}^2$

, Please see Hankinson et al (1999) for formulae for other races and age categories

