## Statistical Analysis Plan

### Baseline

Baseline is defined as the last non-missing assessment before the first dose of CVT-301 in study CVT-301-004 for the patients who received CVT-301 in CVT-301-004 and as the last non-missing assessment before the first dose of CVT-301 in CVT-301-004E for the rest of the patients.

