#### 9.1. SPIROMETRY

For CVT-301-naïve patients and [CVT-301-009](#) patients, spirometry will be assessed at the neurology sites for screening and TV1 and the pulmonary sites will be exclusively responsible for the conduct of spirometry after TV1 (within 2 weeks prior to the 3-, 6-, 9-, and 12-month visits, and 4 to 5 weeks following completion of Treatment Visit 6 [TV6]). For patients from [CVT-301-004](#), spirometry will be assessed at the neurology sites at TV1, and the pulmonary sites will be exclusively responsible for the conduct of spirometry after TV1 as described for the CVT-301-naïve patients. Spirometry data obtained in the study site will reviewed by a central spirometry laboratory (Biomedical Systems, Inc.) which will provide a quality over read of all evaluations based on acceptability and repeatability metrics in accordance with ATS criteria. FEV1, FVC and FEV1/FVC ratio will be recorded from the single “best test” (based on effort with highest summed FEV1 and FVC). Variables will include the absolute FEV1, FVC, and FEV1/FVC ratio and FEV1 and FVC expressed as % of predicted value.

The variables from pulmonary laboratory will include the FEV1, FVC, FEV1/FVC ratio, DLCO, IVC, SVC and VA. FEV1 and FVC expressed as % of predicted value, predicted DLCO, hemoglobin (Hb) adjusted predicted DLCO, and DLCO expressed as % of these predicted values will be calculated per the method in [section 6.2](#). The following analysis will be performed:

All the parameters collected at the pulmonary laboratory as well as the % of predicted DLCO and % of Hb adjusted predicted DLCO will be summarized descriptively by treatment group and overall. In addition, the data will be summarized by treatment/study group.

- Change from baseline to other visits for each parameter.
- Number and percentage of patients with FEV1/FVC < 60% and <70% by visit
- DLCO data will also be provided to indicate whether specific determinations met American Thoracic Society (ATS) quality criteria. The proportion of DLCO/spirometry data measurements meeting or not meeting ATS quality criteria will be summarized by treatment group and overall.

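### Read literally, the SAP pairs facility FEV1 and FEV1/FVC follow-up with a neurology-site TV1 baseline, leaves 004 placebo rollovers without a DLCO baseline, and models a Month 1 at which 004E schedules no lung function test

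*SAP*

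**What the plan says.** **Baseline.** SAP 6.2 gives one general definition. For patients given CVT-301 in study 004, it is the most recent value preceding their first dose there. Otherwise it is "the last non-missing assessment before the first dose of CVT-301 in CVT-301-004E for the rest of the patients". No test site or motor state is named. For the primary spirometry endpoints SAP 4.1 adds: "Changes from baseline (TV1) for each variable will be calculated at each subsequent visit".

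**Where tests are done.** SAP 9.1 states for 004 rollovers that "spirometry will be assessed at the neurology sites at TV1, and the pulmonary sites will be exclusively responsible" for spirometry after that visit, and naive patients follow the same pattern. Protocol 11.1.6 agrees: "All other spirometry assessments will be collected during the DLco and spirometry visits that take place at the pulmonary function lab". At TV1 the neurology site tests on arrival (preferably ON) and again just before a dose taken in the OFF state: "Immediately pre-dose, perform a spirometry assessment" (Protocol 10.1.3.2 and 10.1.3.3). Naive and 009 patients also attend a facility between SV2 and TV1 (Protocol 10.1.1.2): "As part of the procedure, a slow vital capacity maneuver will be performed, followed by DLco, and then spirometry". 004E schedules no such visit for 004 rollovers.

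**Models.** SAP 9.1 plans two MMRMs on facility data, one by dose level and one, in 004 rollovers, by study-004 treatment. The table index lists both for FEV1, FEV1/FVC and DLCO. Each models Months 1, 3, 6, 9 and 12. A source-specific baseline rule is written only for the neurology-site summaries. SAP 9 applies the Section 8 visit table to the spirometry analysis. For the 004 placebo group, that table takes the 004E baseline visit as baseline and marks all four study-004 visits as unused.

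**Month 1.** The TV2 procedures (Protocol 10.1.3.5 and Appendix 6) contain no spirometry or DLco, only the booking of the next facility visit: "Clinic staff will also schedule the DLco and spirometry visit within 2 weeks prior to TV3".

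**The concern.** The primary objective is a within-group change in lung function with no concurrent control. If baseline comes from one setting and follow-up from another, any systematic difference between them is reported as change on treatment. The two streams differ in identifiable ways. Neurology sites are supplied with spirometers, whereas facilities use "their own equipment to perform all necessary pulmonary function testing relevant to DLco acquisition" (Protocol 11.1.7). The data go to different central reviewers. Facility tests are meant to be done ON, whereas the last test before the first dose precedes OFF-state dosing. Because the SAP does not settle the source, two programmers could follow it and report different primary results.

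The Month 1 level raises a separate problem. The models ask for estimates where most patients have no scheduled data, and the imputation step would supply values for tests nobody was due to have.

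**Working it through.** The plan has no figure to reproduce here: no SD, effect size or power is given, and SAP 3.5 says the sample size was not formally calculated. The check is therefore of text, pass-through and estimability.

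**1. Baseline selected by the literal wording (FEV1, FEV1/FVC)**

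| Group in the MMRMs | Baseline as written | Facility tests scheduled in 004E before the first 004E dose | 004E follow-up |
|---|---|---|---|
| Naive (including 005) | TV1, neurology site (SAP 4.1, 6.2) | 1 | Facility |
| 004 placebo rollovers | 004E TV1, neurology site (SAP 4.1, 6.2, 8) | 0 | Facility |
| 004 active rollovers | Study-004 value; source not shown | 0 | Facility |

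**2. Pass-through of an offset.** Let g be the facility reading minus the neurology-site reading at equal lung function. For a mismatched patient, observed change = true change + g. A baseline covariate adjusts for differences between patients; it does not remove a constant shift. In the dose-level model, treatment/study group is additive and default LSMEANS weights its three levels equally. With a slope of 1 for follow-up on baseline:

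- one group mismatched: g × 1/3 = 0.333g on every dose-by-visit LS mean;
- two groups mismatched: g × 2/3 = 0.667g;
- DL2 minus DL1: 0.000.

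With an assumed slope of 0.85 and four assumed group splits, the shifts were 0.30–0.38g and 0.63–0.68g.

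A simulation with every patient mismatched and an assumed true change of −0.05 L shows the mechanism only. For assumed g of −0.10, −0.05, 0, +0.05 and +0.10 L, the LS mean change was −0.148, −0.101, −0.050, 0.000 and +0.050 L. With a facility baseline it was about −0.05 L throughout. The dose difference stayed within 0.005 L of zero.

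**3. DLCO.** It is measured only at facilities, so sources cannot be mixed. Naive patients have the pre-TV1 value. Placebo rollovers have none scheduled in 004E before dosing, and Section 8 sets aside their study-004 visits. Followed as written, that leaves them no DLCO baseline.

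**4. Month 1.** Three groups × five visits = 15 cells. The placebo and naive Month 1 cells have no scheduled data, so 2 are empty by design. Section 8 fills the active cell from study-004 Week 4.

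Rollover model: 10 arm-by-visit cells + baseline (1) + two strata (2) + dose level (1) gives rank 14.

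- Placebo Month 1 empty: 9 + 4 = 13. The placebo Month 1 LS mean and the Month 1 difference are not estimable.
- Month 1 empty in both arms: 8 + 4 = 12. There is no Month 1 result.

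Dose-level model: 10 dose-by-visit cells + baseline (1) + strata (2) + treatment/study group (2) gives rank 15.

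- Month 1 from 004 active patients only: the rank stays 15, but the Month 1 LS means carry group differences from later visits back through the additive group term.
- No Month 1 data: 8 + 5 = 13. Month 1 is not estimable.

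Months 3 to 12 are estimable in both models, assuming that study-004 Week 12, which Section 8 maps to Month 3 for active patients, supplied facility data.

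In the multiple imputation, a placebo or naive patient with any later value has Month 1 treated as an intermittent gap and filled by MCMC.

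**The case against.** The best reply is that a facility baseline was plainly intended. The SAP 6.2 table for predicted values lists a pre-randomization screening row, TV3 to TV6 and the post-TV6 visit, with no TV1 or Month 1 row, which is the facility schedule. Protocol 7 speaks of a baseline DLco before TV1, and spirometry is part of that visit. The MMRM tables are titled as facility data, and SAP 9.1 handles neurology-site data in a separate block. For naive patients this is persuasive on intent. It does not resolve the conflict with SAP 4.1, and it gives placebo rollovers nothing, since Section 8 sends them to a visit with neurology-site spirometry only.

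Three further points stand. The neurology-site rule prefers the arrival value and then an ON-state value, so use of the pre-dose test is possible, not certain. Protocol 11.1.7 says facility spirometry is conducted in the same manner as at clinical sites, so the offset may be small or nil. The imputation is a sensitivity analysis.

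A reader might also infer more than the documents support:

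- *That the primary result is biased by a known amount.* No offset is given, so no figure in mL, standard errors or coverage can carry weight.
- *That DLCO is source-mismatched.* It has one source.
- *That the active-versus-placebo contrast is biased.* This needs different baseline sources in the two arms, and study 004's testing is not shown.
- *That all five placebo estimates are lost.* This follows only if placebo rollovers have no usable baseline. The planned DLCO table by study-004 treatment suggests that study-004 values exist.

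**Conclusion.** The point holds and should be fixed. For FEV1 and FEV1/FVC, the literal rules put a neurology-site baseline under facility follow-up in two of the three groups in the dose-level model, and the contrary indications are never stated as a rule. Any offset would enter the within-group change and largely cancel in DL1 versus DL2. Its size and direction are unknown, so the severity rests on an ambiguous primary-endpoint definition, not on a demonstrated bias. For DLCO the defect is a missing baseline for placebo rollovers as written. At Month 1, one LS mean and one difference in the rollover model cannot be estimated. The dose-level Month 1 means rest solely on study-004 Week 4 data from 004 active patients, if facility data exist there. Both Month 1 statements depend only on the 004E schedule and the Section 8 mapping.

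**What to change.** 1. In SAP 9.1, with 4.1 and 6.2 aligned, define baseline for facility analyses as the last facility value preceding the first CVT-301 dose: in study 004 for 004 active patients, in 004E for all others. For naive patients, name the pre-TV1 DLco/spirometry visit.
2. Amend the Section 8 table so that a study-004 facility value obtained before the first CVT-301 dose may serve as baseline for 004 placebo rollovers. If none exists, show their values descriptively. Do not use a neurology-site baseline in the active-versus-placebo MMRM unless both arms' baselines share a source; otherwise the amendment would itself create a one-arm mismatch.
3. Remove Month 1 from the between-group results of the facility MMRMs, and from both imputation steps for 004 placebo and naive patients. Keep it for 004 active patients, as a within-group result, only if study-004 Week 4 facility data exist.
4. Optionally, add a sensitivity MMRM limited to patients whose baseline and follow-up share a source.

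The cost is a baseline paragraph, a revised table row, a Month 1 restriction and re-runs of planned tables, plus a source flag if item 4 is adopted. No new data are needed. Some placebo rollovers may drop out of the facility change-from-baseline models. Under SAP 2, an analysis defined after study 004 is unblinded counts as exploratory, so the amendment should record its date relative to that unblinding.

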### Change from baseline

The change from baseline will be calculated for each post-baseline assessment as:

$$\text{Change from Baseline} = \text{Post-baseline value} - \text{Baseline value}$$

### Percent change from baseline

The percent change from baseline will be calculated for specified post-baseline assessments as:

$$\text{Percent Change from Baseline} = \frac{(\text{Post-baseline value} - \text{Baseline value}) * 100}{\text{Baseline value}}$$

### DLCO predicted

DLCO predicted will be calculated by Miller equation. (Miller A, Thornton JC, Warshaw R, Anderson H, Teirstein AS, Selikoff IJ. Single breath diffusing capacity in a representative of Michigan, a large industrial state. Am Rev Resp Dis 1983; 127: 270-277).

- Men predicted DLCO =  $12.9113 - (0.229 \times \text{age}) + (0.418 \times \text{height})$
- Women predicted DLCO =  $2.2382 - (0.1111 \times \text{age}) + (0.4068 \times \text{height})$

where age is the age at baseline, height is measured in inches.

### DLCO Predicted, adjusted for Hb

DLCO predicted adjusted for Hb is calculated using the Cotes method, according to the 2005 ATS/ERS guidelines for DLCO.

- DLCO predicted, adjusted for Hb in adult men:  
$$DLCO_{\text{predicted for Hb}} = DLCO_{\text{predicted}} * 1.7 * Hb / (10.22 + Hb)$$
- DLCO predicted, adjusted for Hb in adult women:  
$$DLCO_{\text{predicted for Hb}} = DLCO_{\text{predicted}} * 1.7 * Hb / (9.38 + Hb)$$

## Statistical Analysis Plan

where  $DLCO_{\text{predicted}}$  is the DLCO calculated from Miller equation; Hb = hemoglobin, measured in g/dL. The Hb closest to the date/time of DLCO taken will be used.

### Percent predicted of FEV1 and FVC

The percent predicted of FEV1 and FVC will be calculated using the following equation.

$$\text{Percent Predicted} = 100 * (\text{Observed}) / \text{Predicted}$$

where the predicted value is the value calculated based on formulae by [Hankinson et al \(1999\)](#). The details are listed in table below.

DLCO predicted , percent predicted of FEV1 and FVC	In case a variable used to calculate the predicted value (age, height, Hb) is missing, the following imputation rules will be used in order to calculate the predicted value:
Screening (prior to randomization)	Age, height or Hb from TV1 or the value closest to the date of DLCO/FEV1/FVC assessment if the value at TV1 is missing
TV3, within 2 weeks prior to 3	Age, height or Hb from TV3 or the value closest to the date of DLCO/FEV1/FVC assessment if the value at TV3 is missing
TV4, within 2 weeks prior to 6	Age, height or Hb from TV4 or the value closest to the date of DLCO/FEV1/FVC assessment if the value at TV4 is missing
TV5, within 2 weeks prior to 9	Age, height or Hb from TV5 or the value closest to the date of DLCO/FEV1/FVC assessment if the value at TV5 is missing
TV6, within 2 weeks prior to 12	Age, height or Hb from TV6 or the value closest to the date of DLCO/FEV1/FVC assessment if the value at TV6 is missing
4 to 5 weeks after TV6	The latest non-missing Hb closest to the date of DLCO/FEV1/FVC assessment taken.

